10.4.1.2 Sample Collection, Preparation, Labeling, and Storage

All PK samples must be shipped to the designated central laboratory for storage and batches of samples will be shipped to the analytical testing laboratory. Details of the collection, storage, handling, and shipping of all samples are provided in the Central Laboratory Manual sent to investigative sites prior to the study initiation visit.

10.4.2 Immunogenicity Assessments

Immunogenicity assessments for detection of antibodies against KHK4083 will be evaluated from samples collected from all subjects during the study.

Serum samples will be collected before the initial dose of investigational product at specified collection time windows at Week 0 (Baseline, Day 1) and at all visit weeks during Induction Therapy (pre-dose at Weeks 2, 4, 6, 8, and 10); at the End-of-Induction Therapy visit (only for subjects not continuing to OLE/LTE Therapy); during the Induction Therapy Follow-up Period (only for subjects not continuing to OLE/LTE Therapy) visits (Weeks 16, 20, and 26); during OLE/LTE Therapy (pre-dose at Weeks 12, 16, 20, 24, 28, 32, 36, 40, 44, and 48); at the End-of-OLE/LTE Therapy visit (Week 52); and during the OLE/LTE Therapy Follow-up Period visits (Weeks 56, 60, and 64) as described in the visit schedule for sample collection in Table 9-1 and Table 9-2.

Details of the collection, storage, handling, and shipping of all samples are provided in the Central Laboratory Manual that will be sent to investigative sites prior to the study initiation visit.

10.4.3 Other Potential Study Assessments

For future exploratory biomarker analyses, whole blood samples will be collected as described in the visit schedule for sample collection in Table 9-1 and Table 9-2. All samples

will be labeled and maintained in frozen storage conditions according to the instructions provided in the Central Laboratory Manual.

10.5 Medical/Surgical History, Medication History, and Demographics

Subject demographics (race, ethnicity, sex, and age), medical history including vaccinations (within previous 6 months), current medical conditions, diagnosed chronic conditions, and conditions resolved within the past year will be recorded in detail at the Screening visit. The subject's surgical history particularly previous surgery for UC or other major or abdominal surgery, and anticipated requirement for surgery for UC or other major surgery will also be recorded at the Screening visit (refer to Section 9.1).

Any prior biologic treatment or prior investigational products or therapies including the reason for discontinuation of treatment and all medications for treatment of UC taken within 6 months prior to Screening; and any other previous medication taken 1 month prior to Screening will be documented in detail. Refer to products listed in Inclusion Criteria (Section 7.2) and Exclusion Criteria (Section 7.3); and to Section 8.5 and Section 8.5.1 (prohibited medications) for additional medication details during the Screening and Treatment Period.

Additional background information will be recorded at Screening including tobacco, alcohol, active marijuana (medicinal or recreational), and illicit substance use; allergies/hypersensitivities; and probiotic use and special diet for UC.

10.6 Safety Assessments

All subjects will be assessed regularly for potential occurrence of AEs from the time of signing the ICF until 16 weeks after the last dose of investigational product or any time thereafter if a causal relationship is suspected.

The following information will be collected to evaluate the safety profile of the study population:

- Clinical laboratory evaluations (serum chemistry, hematology, coagulation profile, and urinalysis);
- Vital signs and body weight;
- 12-lead ECG;
- Physical examination; and
- Adverse events (including SAEs).

10.6.1 Clinical Laboratory Evaluation

Clinical laboratory parameters assessed in this study are displayed in Table 10.6.1-1. The collection times for blood, urine, and fecal specimens during the study are specified in Table 9-1 and Table 9-2.

Table 10.6.1-1 Clinical Laboratory Assessments

Serum Chemistry^a	SGOT (AST) SGPT (ALT) Creatine kinase LDH Alkaline phosphatase Total bilirubin Folate Glucose	Creatinine Albumin BUN Sodium Potassium Calcium Vitamin B12	Chloride Total cholesterol Triglycerides Uric Acid Amylase Lipase
wr-CRP Assay	To be performed on serum chemistry samples at Week 0 (Baseline), all visits during Induction Therapy, Week 26 (only for subjects not continuing to OLE/LTE Therapy), and at Weeks 24, 36, 52, and 64.		
Multiplex-31 Assay	To be performed at Baseline (Week 0), Week 2, Week 12, and Week 52 or at a follow-up visit if the subject does not continue in OLE/LTE Therapy.		
Diabetes Screening	Subjects with glycated serum hemoglobin A1c \geq 9% will be excluded from the study.		
Coagulation Profile	prothrombin time partial thromboplastin time		
Hematology^a	Hemoglobin Hematocrit RBCs	WBC count Differential and absolute counts Platelet count	
Urinalysis	Color Specific Gravity pH Protein Glucose Ketones	Bilirubin Urobilinogen Occult blood Nitrites Microscopic examination, if clinically indicated, including RBCs, WBCs, casts, bacteria and crystals	
Urine Drug Screening	Barbiturates, Benzodiazepines, Amphetamines, Cocaine, Cannabinoids, Opiates, Methamphetamine, Alcohol, and Cotinine		
Serum FSH Test	To be performed on all presumed post-menopausal females at Screening. Post-menopausal females are defined as females with the complete absence of menses for 24 consecutive months; have an FSH level $>$ 25 mIU/mL (or in postmenopausal range per local laboratory standards) in the absence of hormone replacement therapy.		
Serum and/or Urine Pregnancy Test (minimum sensitivity 25 IU/L or equivalent units of β -HCG)	To be performed for all female subjects considered to be women of childbearing potential at Screening and at specified timepoints during the Treatment Period. Note: Subjects are considered to not be of childbearing potential if they are \geq 50 years of age and without menses for 24 consecutive months and have an FSH level $>$ 25 mIU/mL (or in postmenopausal range per local laboratory standards); or have undergone a hysterectomy and/or a bilateral salpingo-oophorectomy.		
Hepatitis B and C, and HIV testing	hepatitis B surface antigen or hepatitis B core antibody hepatitis C antibody (If positive, do reflex to RNA by RT-PCR testing) HIV-1 antibodies, HIV-1 antigen, HIV-2 antibody		

Table 10.6.1-1 Clinical Laboratory Assessments

Tuberculosis Screening using PPD Skin Test (by investigative site) and/or IGRA (clinical laboratory) (See details in Section 7.3, Exclusion Criterion 16)
	
Standard PPD skin test or IGRA (but not both) to be performed at Screening at investigative site. If positive (i.e., PPD measures > 5 mm induration), follow up after Screening is required. An IGRA is to be performed at Screening if a subject has a history of positive PPD.
 
Note: Performing of both IGRA and PPD tests in the same subject should be avoided as Screening procedures. Positivity of one of the tests cannot be voided by negativity of the other, i.e., subjects with positive PPD and negative IGRA test performed as a part of Screening will be considered TB positive and will be required to start prophylactic anti-TB therapy prior to infusion of investigational product according to local treatment standards. All safety laboratory tests may be repeated. Screening procedures may be extended by 2 weeks.

Delayed-Type Hypersensitivity Skin Test
	
At investigative sites in the US and other identified countries, the skin tests are to be performed at Screening and Week 10. The skin testing site will be read within 48 to 72 hours following intradermal injection of the Candida albicans antigen. The largest diameter of induration will be measured in mm and collected.

Fecal Sample Analysis
	
Stool cultures to identify enteric pathogens, ova and parasite evaluations, and Clostridium difficile assays are to be performed at Screening, Week 12, and Week 52. Refer to PD assessments for fecal calprotectin measurements at Baseline (Week 0) and Weeks 2, 12, and 52.

a: A subject will be excluded from the study if a specific serum chemistry or hematology value at Screening is outside of the acceptable range as defined in Section 7.3, Exclusion Criteria.

ALT=alanine aminotransferase; AST=aspartate aminotransferase; BUN=blood urea nitrogen; β-HCG=beta human chorionic gonadotrophin; ; FSH=follicle-stimulating hormone; HIV=human immunodeficiency virus; IGRA=interferon gamma release assay; LDH=lactate dehydrogenase; LTE=long-term extension; OLE=open-label extension; PD=pharmacodynamic(s); PPD=purified protein derivative; RBC=red blood cell; RNA=ribonucleic acid; RT-PCR=Real-time reverse transcription-polymerase chain reaction; SGOT=serum glutamic-oxaloacetic transaminase; SGPT=serum glutamic-pyruvic transaminase; TB=tuberculosis; US=United States; WBC=white blood cell; wr-CRP=wide-range C-reactive protein.

Any clinically important abnormal laboratory values noted at the Screening visit will be recorded as medical history. In addition, in order for the Sponsor to collect additional information about clinically important laboratory abnormalities, at minimum, the following laboratory abnormalities should be captured as appropriate:

- Any laboratory test result that meets the criteria for an SAE;
- Any laboratory abnormality that requires the subject to have study treatment discontinued or interrupted;
- Any laboratory abnormality that requires the subject to receive specific corrective therapy.

All clinically important abnormal laboratory tests occurring during the study will be repeated at appropriate intervals until (1) the value returns to baseline, (2) the value is judged to be clinically acceptable by the Investigator and the Sponsor, or (3) a diagnosis that explains the

abnormal laboratory value is made. When possible, the Investigator should report the clinical rather than the laboratory term (e.g., anemia versus low hemoglobin).

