A review of the subject's prior medical history of neoplasias and infections, and evaluation for active TB and demyelinating diseases, testing for hepatitis B viral infection and latent infection should be conducted. (Silva, 2010)

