- 11) Subject has clinically significant cardiac disease (class II, III, or IV of the New York Heart Association [NYHA] classification) (The Criteria Committee of the NYHA Nomenclature and Criteria for Diagnosis of Diseases of the Heart and Great Vessels, 1994); unstable angina pectoris; myocardial infarction within 6 months or is post angioplasty or stenting within 6 months; uncontrolled hypertension; or clinically significant abnormality, such as cardiac arrhythmia, on a 12-lead electrocardiogram (ECG) at Screening;
- 12) Subject is pregnant or breastfeeding;
- 13) Subject has had major immunologic reaction (e.g., serum sickness, anaphylaxis, or anaphylactoid reaction);
- 14) Subject is Hepatitis B core antibody or surface antigen positive at Screening and/or Hepatitis C antibody positive with detectable RNA at Screening;
- 15) Subject has a history of human immunodeficiency virus (HIV) positivity, tests positive for HIV at Screening, or has congenital or acquired immunodeficiency;
- 16) Subject has or has had active TB, suspected extra-pulmonary TB, a history of incompletely treated TB, or latent TB or other latent infection. Subjects with latent TB (purified protein derivative [PPD] or interferon gamma release assay [IGRA]) may be included in the study if prophylactic therapy for latent TB is started at least 4 weeks prior to Screening. Subjects with a potentially untreated other infection (clinical findings) are to be excluded.

Note: Performing of both IGRA and PPD tests in the same subject should be avoided as screening procedures. Positivity of one of the tests cannot be voided by negativity of the other, i.e., subjects with positive PPD and negative IGRA test performed as a part of Screening will be considered TB positive and will be required to start prophylactic anti-TB therapy prior to infusion of investigational product according to local treatment standards. All safety laboratory tests may be repeated. Screening procedures may be extended by 2 weeks.

- 17) Subject has bacterial infections requiring treatment with oral or parenteral antibiotics (topical antibiotics are allowed), within 2 and 4 weeks, respectively, of the Screening period;
- 18) Subject has a history of systemic opportunistic infection or recurrent infections;

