Height	X										
12-lead ECG	X	X ^e				X ^e	X ^e				
Hematology (CBC with diff & platelets)	X	X	X	X	X	X	X	X	X	X	X
Serum Chemistry Profile	X	X	X	X	X	X	X	X	X	X	X
Coagulation Profile	X	X						X			
Multiplex-31 Assay ^f		X	X					X			
Urinalysis	X	X	X	X	X	X	X	X	X	X	X
Serum FSH ^g	X										
Serum Pregnancy ^g	X										
Urine Pregnancy ^g		X		X		X		X	X	X	X
Urine Drug Screen	X										

Table 9-1 Study Schedule of Events - Screening, Induction Therapy, and Follow-up Period

Procedure	Screening Day -28 to Day -1	Treatment Period - Double-blind Induction Therapy: Weeks 0 to 12 (Last dose at Week 10) ^a (All Randomized Subjects)						Induction Therapy Post-treatment Follow-up Period for Subjects Not Enrolling in OLE Therapy			
		Baseline						End-of- Induction Therapy	Follow- up 1	Follow- up 2	Follow- up 3
		Week 0 Day 1	Week 2 ± 2 days	Week 4 ± 4 days	Week 6 ± 4 days	Week 8 ± 4 days	Week 10 ± 4 days	End-of- Treatment Week 12 ± 4 days	Week 16 ± 7 days	Week 20 ± 7 days	End-of- Study Week 26 ± 7 days
Stool Enteric Pathogens (including Clostridium difficile)	X							X			
Hemoglobin A1c	X										
HIV Test; Hepatitis B (core antibody or surface antigen); Hepatitis C antibody	X										
PPD (or QuantiFERON)- TB ^h	X										
Delayed-type Hypersensitivity Skin Test ⁱ (US and other selected countries)	X						X				
Randomization		X									
Diary Training	X										
Partial Mayo Clinic Score (without sigmoidoscopy, includes review of diary) with Physician's Global Assessment		X	X	X	X	X	X	X	X	X	X

Table 9-1 Study Schedule of Events - Screening, Induction Therapy, and Follow-up Period

Procedure	Screening Day -28 to Day -1	Treatment Period - Double-blind Induction Therapy: Weeks 0 to 12 (Last dose at Week 10) ^a (All Randomized Subjects)							Induction Therapy Post-treatment Follow-up Period for Subjects Not Enrolling in OLE Therapy		
		Baseline						End-of- Induction Therapy	Follow- up 1	Follow- up 2	Follow- up 3
		Week 0 Day 1	Week 2 ± 2 days	Week 4 ± 4 days	Week 6 ± 4 days	Week 8 ± 4 days	Week 10 ± 4 days	End-of- Treatment Week 12 ± 4 days	Week 16 ± 7 days	Week 20 ± 7 days	End-of- Study Week 26 ± 7 days
Flexible Sigmoidoscopy with biopsy for mMES, UCEIS, modified Baron score & total Mayo Clinic score (includes review of diary)	X (within 7 to 28 days prior to first dose)							X ^j (recommend 7 to 13 days prior to Week 12 LTE dosing)			
IBDQ		X	X	X	X	X	X	X	X	X	X
Fecal Calprotectin ^k		X	X					X			
wr-CRP Assay		X	X	X	X	X	X	X			X

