- Medical and Surgical History - including concurrent illnesses; chest x-ray if needed (within previous 3 months) results, vaccinations (within previous 6 months), previous surgery for UC or other major or abdominal surgery, and anticipated requirement for surgery for UC or other major surgery;
- Childbearing potential;
- Complete physical examination (Section 10.6.4);

- Vital Signs (systolic and diastolic blood pressure, radial pulse, and respiration rate) and body temperature (oral) (Section 10.6.2);
- Body weight and height (Section 10.6.4);
- 12-lead ECG (Section 10.6.3);
- Previous treatment with corticosteroids, immunosuppressive medications or TNF antagonist therapy, any prior biologic treatment (e.g., infliximab, adalimumab, or golimumab), and prior investigational products or therapies (Section 8.5);
- Prior and concurrent prescriptions and non-prescription medications, including any other UC treatments such as probiotics and other over-the-counter medications and supplements. Stable doses of aminosalicylates, oral glucocorticoids, azathioprine, and 6-mercaptopurine are permitted as described in Section 8.5 (refer to Section 8.5.1 for prohibited medications);
- Tobacco use, alcohol use, active marijuana (medicinal or recreational) use, illicit substance use;
- Allergies/hypersensitivities;
- Diet special for UC;
- Pre-treatment AEs (Section 10.6.5);
- Clinical Laboratory Evaluations (Table 9-1; refer to Section 10.6.1 for list of tests): Blood samples will be drawn at Screening for serum chemistry, hematology, coagulation profile, serum pregnancy, hepatitis B and C, and HIV testing; TB screening will be performed using a PPD skin test or IGRA; urine samples will be collected for analysis and urine drug screen; and fecal samples will be collected (before the start of the preparations required for the sigmoidoscopy or as specified in the stool collection instruction section of the laboratory manual) for analysis, i.e., cultures for enteric pathogens, ova and parasite evaluation, and *Clostridium difficile* assay.
- Delayed-type hypersensitivity skin test with the *Candida albicans* antigen - at all investigative sites in the US and in other selected countries (Section 10.4.1). The skin testing site will be read within 48 to 72 hours following intradermal injection of the antigen. The largest diameter of induration will be measured in mm and recorded.

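### Exclusion 14 needs both hepatitis B results, but the two screening test lists name the markers as alternatives

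*Protocol*

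**What the plan says.** The eligibility rule is in Section 7.3, Exclusion 14, and is repeated in the Synopsis. A subject is out if "Subject is Hepatitis B core antibody or surface antigen positive at Screening"; the criterion goes on to a separate hepatitis C condition.

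Three places tell a site what to test:

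- Table 10.6.1-1, hepatitis and HIV row: "hepatitis B surface antigen or hepatitis B core antibody".
- Table 9-1, Screening column: "HIV Test; Hepatitis B (core antibody or surface antigen); Hepatitis C antibody".
- Section 9.1: "Blood samples will be drawn at Screening for serum chemistry, hematology, coagulation profile, serum pregnancy, hepatitis B and C, and HIV testing". No hepatitis B marker is named here, and the reader is sent to Section 10.6.1 for the list of tests.

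Nothing else in the protocol or SAP requires both hepatitis B markers for each subject. Section 4.2, reviewing existing treatments, says "testing for hepatitis B viral infection and latent infection should be conducted", but this is background drawn from a cited review and not a study procedure.

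**The concern.** The same word does opposite work in the two kinds of text. In an exclusion rule, *or* widens the exclusion, because either positive result is enough. In a list of tests, *or* narrows the work, because either test is enough. A site that follows both tables to the letter can finish every listed hepatitis B test and still not know whether Exclusion 14 is met.

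The checks on eligibility do not close the gap by themselves. Section 9.1 requires that no exclusion criterion is met, and Sections 9 and 9.2 require Screening results to be reviewed before randomisation. A review of results cannot reveal a positive marker that was never ordered. What is at stake is that a subject whom the protocol means to exclude could be enrolled and dosed. This is a matter of eligibility and subject safety; it does not bear on the efficacy estimate.

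**Working it through.** The plan states no figure to reproduce, so the check sets the test lists against the criterion.

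**Step 1. What the criterion needs.** There are four possible patterns of the two markers. Exclusion 14 applies to three of them.

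| Surface antigen | Core antibody | Excluded by criterion 14? | Detected by surface antigen alone? | Detected by core antibody alone? | Detected by both tests? |
|---|---|---|---|---|---|
| + | + | Yes | Yes | Yes | Yes |
| + | − | Yes | Yes | **No** | Yes |
| − | + | Yes | **No** | Yes | Yes |
| − | − | No | – | – | – |

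Each single-marker screen detects 2 of the 3 excludable patterns and misses 1. Surface antigen alone misses antigen-negative/core-positive. Core antibody alone misses antigen-positive/core-negative. Only the pair of results detects all 3.

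**Step 2. What the test lists supply.** Tables 10.6.1-1 and 9-1 both use *or*, in opposite marker order, so this is not a slip in one cell. Section 9.1 leads back to Section 10.6.1 and adds nothing.

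**Step 3. Whether the literal reading is a fair one.** The tuberculosis row of Table 10.6.1-1 uses *or* for genuine alternatives: "Standard PPD skin test or IGRA (but not both) to be performed at Screening". In the same cell as the hepatitis B line, the HIV tests form a plain list without *or*: "HIV-1 antibodies, HIV-1 antigen, HIV-2 antibody". A site could reasonably take the hepatitis B line as a choice.

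**Step 4. Size.** The documents give neither the prevalence of any marker pattern nor the share of subjects who would be tested for one marker only. The number affected among about 60 subjects cannot be calculated from them.

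**The case against.** The strongest reply is that the criterion governs and already demands both results. An investigator holding one result cannot confirm Exclusion 14, and the tables look like shorthand for the criterion's own phrase rather than a decision to allow one test. The tuberculosis row can also be turned round: where the table means strict alternatives it says so expressly, and the hepatitis B line carries no such restriction. A Central Laboratory Manual exists (Sections 10.4.1.2 and 10.4.2). If it sets a fixed panel with both markers, sites make no choice at all.

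This has weight. It makes the likely practical effect smaller, and it means the documents cannot show that single-marker testing occurs. It does not remove the mismatch, because no text available here requires both markers.

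Three stronger readings are tempting, and the documents do not support them:

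- *Different sites would reach opposite decisions on the same patient.* This depends on who runs the serology and on the manual's contents, neither of which the documents settle.
- *The problem would go unseen centrally.* Section 6.3 provides regular medical monitoring meetings that cover the inclusion and exclusion criteria. SAP Sections 5.2 and 9.6 provide for review of protocol deviations and a listing of eligibility violations. These would not find an untested positive, but a missing marker result could be noticed.
- *The protocol identifies hepatitis B reactivation as a risk of this drug.* Section 4.2 names it for TNF-alpha blockers, not for KHK4083, and no passage states the reason for Exclusion 14.

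**Conclusion.** The point holds as an inconsistency between a stated exclusion rule and the tests listed to apply it. Read literally, the protocol permits a hepatitis B screen that leaves 1 of 3 excludable patterns undetected. This rests on taking *or* in the two tables at face value and on the absence of any other text requiring both markers. The unseen laboratory manual could resolve it in practice.

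A reader might try to size it by assuming a prevalence p of antigen-negative/core-positive subjects and surface-antigen-only testing for everyone. With assumed p from 1% to 10%, 60p gives 0.6 to 6 subjects, and 1 − (1 − p)^60 gives a 45% to 99.8% chance of at least one. That is a worst case built on two assumptions and not an estimate. If only a fraction f were tested that way, the expected number is 60pf; with p = 2% and f = 10%, it is 60 × 0.02 × 0.10 = 0.12. Core-antibody-only testing, which the literal text equally permits, would detect these subjects. No such figure should be cited as the size of the problem.

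No endpoint, estimate, sample size or error rate is affected. The correction is still worth making, because it concerns subject safety and costs little.

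**What to change.** Reconcile the hepatitis B entries in Table 9-1 and Table 10.6.1-1 with Exclusion 14 in Section 7.3 and the Synopsis, so that the listed screening tests supply every result the criterion relies on and those results are available before randomisation. Check the Central Laboratory Manual against the reconciled text. Whether the test lists or the criterion changes is the sponsor's decision.

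If the test lists change, the cost is a few words in two tables and at most one more marker on the blood sample already drawn at Screening. If the manual already specifies both markers, the edit only brings the protocol into line with practice.
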